Window (days)	-28 to 0	--	± 3	± 3	± 3	± 3	± 3	± 3	± 3	± 3	± 3	± 3	± 7	± 7	± 7
Informed consent ^a	X														
Medical, cancer history ^d	X														
Physical examination	X			X	X	X	X	X	X	X	X	X	X	X	
Pregnancy test (serum or urine) ^e	X ^e			X	X	X	X	X	X	X	X	X	X		
ECOG performance status	X			X	X	X	X	X	X	X	X	X	X	X	
Vital signs (see Section 8.2.3) ^f	X	X		X	X	X	X	X	X	X	X	X	X	X	
Body weight	X	X		X	X	X	X	X	X	X	X	X			
Hematology (see Table 10)	X		X	X	X	X	X	X	X	X	X	X	X	X	
Clinical chemistry (see Table 10)	X		X	X	X	X	X	X	X	X	X	X	X	X	
Urinalysis	X		X	X	X	X	X	X	X	X	X	X	X	X	
12-lead ECG	X														
Tumor markers ^g	X			X	X	X	X	X	X	X	X	X	X		
cfDNA (blood) ^h	X			X									X		
Circulating soluble analytes ⁱ	X	X	X	X	X	X							X		
Blood immune biomarkers ⁱ	X	X	X	X	X	X							X		
Stool collection ^j	X			X											
Tumor biopsy ^k	X ^l	As early as possible after the 2nd dose ^k of ipilimumab and after the 4th dose of ipilimumab													
Concomitant medications ^m	X	X	X	X	X	X	X	X	X	X	X	X	X	X	X
Adverse events ^m	X	X	X	X	X	X	X	X	X	X	X	X	X	X	X
Nivolumab administration ⁿ		X		X	X	X	X	X	X ^o	X	X	X			
Ipilimumab administration ⁿ		X		X		X		X							

Tests & Procedures	Screening ^a	On-Treatment Evaluations											End of Treatment	Follow-up	
		C1	C2	C3	C4	C5	C6	C7	C8	C9	C10				
Day	0	D1	D8	D1	D1	D1	D1	D1	D1	D1	D1	D1	15-30 days after last dose	First visit (90 days after last dose) ^b	Q3M for 2 years ^c
Window (days)	-28 to 0	--	± 3	± 3	± 3	± 3	± 3	± 3	± 3	± 3	± 3	± 3	± 7	± 7	± 7
Follow-up for overall survival ^c														X	X
Assess subsequent cancer therapy													X	X	X
Disease assessment ^p	X	Cycle 4 Day 1, then beginning at Cycle 6 Day 1, repeat every 8 weeks (± 7 days) until radiographic progression or the start of subsequent therapy, whichever comes first													

cfDNA = cell-free deoxyribonucleic acid; Cx = Cycle x; ECG = electrocardiogram; ECOG = Eastern Cooperative Oncology Group; Q3M = every 3 months; Q3W = every 3 weeks; Q4W = every 4 weeks; Q6W = every 6 weeks; Q12W = every 12 weeks.

^a Screening evaluations are to be conducted within 28 days of the first dose of protocol therapy. Some screening procedures may occur on Cycle 1 Day 1 as appropriate. Informed consent must be obtained prior to any study-specific procedures and may be obtained prior to the 28-day screening window.

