^m All AEs, SAEs, and all concomitant medications will be collected from the time the participant signs informed consent until 100 days after the last dose of study intervention. Prior to initiation of study intervention, only AEs and SAEs that are related to a protocol mandated intervention, including those that occur prior to assignment of study procedures (eg, screening invasive procedures, such as biopsies) should be reported. Trial-limiting toxicities can be found in [Section 8.3.7](#).

- ⁿ Nivolumab monotherapy will be administered at 360 mg IV Q3W for 4 cycles. Participants who continue to show clinical benefit after the first disease assessment will receive nivolumab at 480 mg IV Q4W until PD or intolerable toxicity (starting at Cycle 5).
- ^o Beginning at Cycle 7, nivolumab maintenance (nivolumab at 480 mg IV Q4W) will be administered until PD or intolerable toxicity.
- ^p Scans will be performed within 7 days prior to Day 1 of Cycle 4, Cycle 6, and every *even* cycle thereafter until death, disease progression, initiation of another systemic anticancer therapy, loss to follow-up, withdrawal of consent, or study termination, whichever occurs first (See [Section 8.1](#)). In addition, ad hoc scans, as part of standard of care, will be collected for participants who have discontinued treatment for reasons other than radiographic progression and prior to any alternate therapies.

Table 3: Schedule of Assessments Advanced Prostate Cancer (Nivolumab Only Arm: Nivolumab 360 mg Q3W and Maintenance 480 mg Q4W)

Tests & Procedures	Screening ^a	On-Treatment Evaluations				End of Treatment	Follow up ^b	
		C1		C2-4	C5 Onwards		15-30 days after last dose	First visit (90 days after last dose) ^b
Day	0	D1	D8	D1	D1			
Window (days)	-28 to 0	--	± 3	± 3	± 3	± 7	± 7	± 7
Informed consent ^a	X							
Medical, cancer history ^d	X							
Physical examination	X			X	X	X	X	
ECOG performance status	X			X	X	X	X	
Vital signs (see Section 8.2.3) ^e	X	X		X	X	X	X	
Body weight	X	X		X	X			
Hematology (see Table 10)	X		X	X	X	X	X	
Clinical chemistry (see Table 10)	X		X	X	X	X	X	
Urinalysis	X		X	X	X	X	X	
12-lead ECG	X							
PSA ^f	X	X	PSA will be collected every cycle throughout treatment			X		
ctDNA (blood) ^g	X			X ^g		X		
Circulating soluble analytes ^h	X	X	X	X		X		
Blood immune biomarkers ^h	X	X	X	X		X		
Stool collection ⁱ	X			X ⁱ				
Tumor biopsy ^j	X ^k			X ^j		X ^j		
Concomitant medications ^l	X	X	X	X	X	X	X	
Adverse events ^l	X	X	X	X	X	X	X	

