- ^o Scans will be performed within 7 days prior to Day 1 of Cycle 4, Cycle 6 and every 8 weeks thereafter until death, disease progression, initiation of another systemic anticancer therapy, loss to follow-up, withdrawal of consent, or study termination, whichever occurs first (See [Section 8.1](#)). In addition, ad hoc scans, as part of standard of care, will be collected for participants who have discontinued treatment for reasons other than radiographic progression and prior to any alternate therapies.
- ^p Optional procedure for participants who consent to participate in the digital PRO using a smartphone application, from consent up to 100 days after the last dose of study intervention. Study Staff to review participant's data via ApricityOncology™, a clinical dashboard website at regular intervals per training materials.

Table 4: Schedule of Assessments Advanced Prostate Cancer (Nivolumab and Ipilimumab Arm: Nivolumab Q3W and Ipilimumab Q6W [Cycles 1 and 2], Followed by Single-agent Nivolumab Q4W)

Tests & Procedures	Screening ^a	On-Treatment Evaluations						End of Treatment	Follow-up (After Date Off Treatment)	
		C1			C2		C3 Onward		15-30 days after last dose	First visit (90 days after last dose) ^b
Day	0	D1	D8	D22	D1	D22	D1			
Window (days)	-28 to 0	--	± 3	± 3	± 3	± 3	± 3	± 7	± 7	± 7
Informed consent ^a	X									
Medical, cancer history ^d	X									
Physical examination	X			X	X	X	X	X	X	
ECOG performance status	X			X	X	X	X	X	X	
Vital signs (see Section 8.2.3) ^e	X	X		X	X	X	X	X	X	
Body weight	X	X		X	X	X	X			
Hematology (see Table 10)	X		X	X	X	X	X	X	X	
Clinical chemistry (see Table 10)	X		X	X	X	X	X	X	X	
Urinalysis	X		X	X	X	X	X	X	X	
12-lead ECG	X									
PSA ^f	X	X	PSA will be collected every cycle throughout treatment					X		
cfDNA (blood) ^g	X			X				X		
Circulating soluble analytes ^h	X	X	X	X	X	X		X		
Blood immune biomarkers ^h	X	X	X	X	X	X		X		
Stool collection ⁱ	X			X ⁱ						
Tumor biopsy ^j	X ^k			X ^j		X ^j		X (optional)		
Concomitant medications	X	X	X	X	X	X	X	X	X	
Adverse events ^l	X	X	X	X	X	X	X	X	X	
Nivolumab administration ^m		X		X	X	X	X ⁿ			
Ipilimumab administration ^m		X			X					
Follow-up for overall survival ^c									X	X

Tests & Procedures	Screening ^a	On-Treatment Evaluations						End of Treatment	Follow-up (After Date Off Treatment)	
		C1			C2		C3 Onward		15-30 days after last dose	First visit (90 days after last dose) ^b
Day	0	D1	D8	D22	D1	D22	D1			
Window (days)	-28 to 0	--	± 3	± 3	± 3	± 3	± 3	± 7	± 7	± 7

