6.6.1.3 Dose Delays and Interruptions for Nivolumab with or without Ipilimumab

Dose delays and interruptions are permitted for toxicity reasons (see [Section 6.6.1.1](#)). Dose delays and interruptions for reasons other than toxicity, such as surgical procedures, may be allowed with Medical Monitor approval. The acceptable length of interruption will depend on agreement between Investigator and Medical Monitor.

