8.1 EFFICACY ASSESSMENTS

Participants will undergo tumor assessments as designated in the SOAs (see [Section 1.3](#)) regardless of dose delays, until loss of clinical benefit as determined by the Investigator (unless the participant withdraws consent or the Sponsor terminates the study). All participants who discontinue study intervention for reasons other than radiographic progression (eg, AEs) will continue tumor assessments until death, disease progression, initiation of another systemic anticancer therapy, loss to follow-up, withdrawal of consent, or study termination, whichever occurs first. At the Investigator's discretion, tumor assessments may be repeated at any time if PD is suspected.

Measurable and evaluable lesions should be assessed and documented at screening. Tumor assessments performed as standard of care prior to obtaining informed consent and within 28 days prior to treatment do not have to be repeated at screening.

Screening assessments must include computed tomography (CT) scans (with IV contrast unless contraindicated and oral contrast as appropriate per institutional standards). A spiral CT scan of the chest may be obtained but is not a requirement. If a CT scan with contrast is contraindicated (ie, in participants with contrast allergy or impaired renal clearance), a non-contrast CT scan of the chest may be performed and magnetic resonance imaging (MRI) scans of the abdomen, pelvis, and head (as applicable) should be performed as applicable.

If a CT scan for a tumor assessment is performed in a positron emission tomography (PET)/CT scanner, the CT acquisition must be consistent with the standards for a full contrast diagnostic CT scan.

Bone scans (technetium-99m [TC-99m]) or sodium fluoride (NaF) PET should be performed at screening if clinically indicated. If bone metastases are present at screening and cannot be seen on CT or MRI scans, or if clinically indicated, TC-99m and NaF-PET bone scans should be repeated when complete response (CR) is identified in target disease or when progression in bone is suspected.

CT scans of the head, neck, or extremities should also be performed if clinically indicated and repeated throughout the study if there is evidence of disease at screening.

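### Tables 1 and 2 give two scan rules, by even-numbered cycle and by 8-week interval; where a site follows the cycle rule, a dosing hold can date progression past 6 months and earn clinical benefit

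*Protocol*

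**What the plan says.** Three places in the protocol govern scan timing in the advanced metastatic arms.

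- Section 1.3, footnote p of Tables 1 and 2: "Scans will be performed within 7 days prior to Day 1 of Cycle 4, Cycle 6, and every" even-numbered cycle after that. This ties every scan to a dosing visit.
- Section 1.3, disease assessment row of the same tables: a scan at Cycle 4 Day 1, "then beginning at Cycle 6 Day 1, repeat every 8 weeks (± 7 days) until radiographic progression". This is a calendar interval, but it starts from two cycle-based anchors.
- Section 8.1, which footnote p cites: assessments follow the schedule tables "regardless of dose delays, until loss of clinical benefit as determined by the Investigator".

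The prostate monotherapy table (Table 3, footnote o) has no even-cycle wording: "Scans will be performed within 7 days prior to Day 1 of Cycle 4, Cycle 6 and every 8 weeks thereafter until death". Only Tables 1 and 2 carry it.

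On the length of a hold, Section 6.6.1.3 sets no maximum for these arms: "The acceptable length of interruption will depend on agreement between Investigator and Medical Monitor".

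SAP Section 5.4.1 measures the duration of stable disease (SD) from first dose to the date of radiographic progression. A duration of at least 6 months counts towards the clinical benefit rate (CBR), a co-primary endpoint.

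**The concern.** A cycle-based rule and a calendar rule agree only while dosing runs on time. Once a dose is held, Day 1 of the next cycle moves, and a scan tied to it moves too. Sites reading the footnote and sites reading the row could scan the same participant weeks apart, and nothing in the documents settles which is right.

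This matters because the co-primary endpoint has a time threshold and progression is dated by the scan that shows it. If the last scan due before 6 months slips past 6 months, progression that it would have shown is recorded after the threshold and the participant becomes a success. The SAP has no safeguard. Its check on the last SD assessment (Section 5.4.1) covers only participants without progression. Its 16-week rule for progression-free survival (Section 5.4.2.2) covers only deaths. The futility rule in Protocol Section 9.3.1.2 counts a missed evaluation window as non-benefit only when no treatment delay explains it, which fits a cycle-based reading and adds to the ambiguity.

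**Working it through.** **Plan's own figures.** CBR of 32/160 with a beta(0.4, 1.6) prior gives a beta(32.4, 129.6) posterior and a 95% interval of 14.2% to 26.5%, as in Protocol Section 9.1. The 8-week interval in the row is also reproduced by the even-cycle rule for monotherapy on time (step 2).

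**1. Cycle starts, in weeks from first dose.** Monotherapy (Table 1) has four 3-week cycles, then 4-week cycles. The combination (Table 2) has six 3-week cycles, then 4-week cycles.

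**2. Scan weeks with no delay.**

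| | Cycle 4 | Cycle 6 | Cycle 8, footnote | Next scan, row (Cycle 6 + 8) |
|---|---|---|---|---|
| Monotherapy | 9 | 16 | 16 + 4 + 4 = 24 | 24 |
| Combination | 9 | 15 | 15 + 3 + 4 = 22 | 23 |

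The combination rules differ by 1 week from Cycle 8 on, because Cycle 6 to Cycle 8 is 7 weeks.

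**3. Hold after Cycle 6 that takes the footnote scan to 6 months.** Neither document gives 6 months in days; 180 to 184 days is assumed. Hold needed = 6 months minus the scheduled day of the scan.

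- Monotherapy, Cycle 8 Day 1 = day 168: 12-16 days, or 19-23 days if the scan is done 7 days before Day 1.
- Combination, Cycle 8 Day 1 = day 154: 26-30 days, or 33-37 days.

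Under the row, with Cycle 6 on time, the latest permitted day is 24 × 7 + 7 = 175 (monotherapy) or 23 × 7 + 7 = 168 (combination). Neither reaches 180.

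Example: a 3-week hold after Cycle 6 on monotherapy moves the footnote scan from week 24 to week 27 (day 189), or to day 182 if it is done 7 days before Day 1. Progression visible at week 24 is then dated at 26 to 27 weeks.

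**4. Hold before Cycle 6.** This shifts the anchor in both rules. A 3-week hold on monotherapy puts Cycle 6 at week 19 and the row's next scan at week 27. A 4-week hold on the combination puts them at weeks 19 and 27. Following the row alone therefore does not remove the problem.

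**5. Upper bound for the combination arm (160 participants).** Assumptions: exponential progression-free survival with a median of 10, 13 or 18 weeks; 10%, 20% or 30% of participants have a hold of at least 6 weeks; every hold falls after Cycle 6; every site follows the footnote; no discretionary scans; nobody affected already has a confirmed response. A 6-week hold puts Cycle 8 at week 28, so the scan falls at week 27 or later.

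- Progression-free at week 15: 0.5^(15/median) = 0.35, 0.45, 0.56.
- Progression by week 23, given that: 1 − 0.5^(8/median) = 0.43, 0.35, 0.27.
- Product: about 0.15 in each case, or about 24 to 25 of 160.
- Times the delay share: 2.4-2.5, 4.8-5.0 and 7.1-7.5 participants, which is about 1.5, 3 and 4.5 points of CBR.

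For scale, the half-width of the planned interval is (26.5 − 14.2)/2, about 6 points. In the smaller monotherapy arm, one reclassified participant is 1/40 = 2.5 points.

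**The case against.** Most of the text favours calendar timing. Section 8.1 says so, and footnote k in both tables tells participants to keep to the planned assessment times whatever happens to dosing. The row and the footnote part company only for holds after Cycle 6, by which time all four ipilimumab doses have been scheduled. Table 7 sends many Grade 3-4 events to permanent discontinuation, so a long hold followed by resumption is only a subset of toxicity. Section 8.1 also allows that "tumor assessments may be repeated at any time if PD is suspected".

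Much of this stands, and it limits the size. It does not settle the rule. Section 8.1 sends the reader to the schedule tables, where both rules sit. Footnote k belongs to the biopsy row. Unscheduled scans are at the investigator's discretion.

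Three stronger readings are tempting and not supported:

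- A reader might infer that CBR will be inflated, and more so with the combination. Protocol Sections 2.2.1 and 2.3 say that adverse events are more frequent and severe with the combination; they say nothing of how often doses are held. The monotherapy arm also needs a shorter hold to cross 6 months, which works the other way. SAP Section 5.4 plans no comparison between groups.
- A reader might take 1.5 to 4.5 points as an estimate. It is a bound. If, for illustration, one third of holds fell after Cycle 6 and half the sites followed the footnote, 5 participants would become 5 × 1/3 × 1/2, about 0.8 of 160, or 0.5 points.
- A reader might infer that participants off drug after toxicity go unscanned. Footnote p alone gives them no scheduled date, only ad hoc standard-of-care scans. Sections 7.1, 7.2 and 8.1 require assessments to continue, and the row's 8-week interval does not depend on dosing once Cycle 6 has passed.

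**Conclusion.** The conflict is real and stands in the current text. Tables 1 and 2 carry two scan rules with no order of precedence, and they differ by 1 week in the combination arm even with no delay.

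Where a site follows footnote p, a hold after Cycle 6 of about 2-3 weeks (monotherapy) or 4-5 weeks (combination) can turn progression before 6 months into clinical benefit under the SAP's SD rule. Progression-free survival is dated late in the same participants. A hold before Cycle 6 does the same under either rule if it is long enough.

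The documents do not show that this will happen or how often. Neither the size nor the direction by arm can be computed, because no delay rate is given. The figure of about 1.5 to 4.5 points rests on every assumption in step 5 of the working and should be read only as a ceiling for those delay shares. The correction is still worth making: it protects a co-primary endpoint at little cost.

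**What to change.** In both the disease assessment row and footnote p of Tables 1 and 2, state scan times in weeks from first dose: weeks 9 and 16 for nivolumab alone, weeks 9 and 15 for the combination, then every 8 weeks ± 7 days. Say that these times do not move with dose delays and that scans continue after discontinuation for reasons other than progression, consistent with Section 8.1. Changing the footnote alone would leave the row anchored to Cycle 4 and Cycle 6 and create a new conflict after any hold before Cycle 6.

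For data already collected, flag scans more than 2 weeks off that schedule and add to the SAP a sensitivity analysis of CBR that excludes SD credit depending on a late scan. The SAP should also define 6 months in days. If it is set at 180 to 182 days, a monotherapy scan 12 to 14 days late reaches the threshold unflagged, and the flag for that arm should then start at the edge of the ± 7-day window.

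The cost is a wording change in two tables, a short memo to sites and one extra analysis. No scheduled scans are added. The small downside is that some scans will no longer coincide with a dosing visit.

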2 INTRODUCTION

2.1 STUDY RATIONALE

The aim of this study is to provide a prospective classification of CD8 high (immunologically “hot”) versus CD8 low (immunologically “cold”) tumors at the time of treatment, based on the percentage of CD8 cells in a tumor biopsy, and to address the predictive value of the CD8 biomarker for selecting patients for treatment with nivolumab with or without ipilimumab.

2.2 BACKGROUND

Immuno-oncology is a promising new area for cancer therapeutics. The immune system is capable of exquisite adaptation and selective targeting, a process that is now being harnessed and directed towards advanced cancer. Immuno-oncology therapies manipulate the immune response against cancer in several ways. Vaccines have been developed with the goal of priming the cellular and humoral immune response towards specific cancer antigens. Other therapies target the specific mechanisms that cancer cells use to avoid detection by the host immune system. These evasion mechanisms take advantage of immune “checkpoints” that regulate the cellular immune response. Many cancer types hijack these mechanisms thereby rendering the immune system unable to mount an effective antitumor immune response.

2.2.1 Immune Checkpoint Inhibitors

Immune checkpoint inhibitors, such as ipilimumab and nivolumab, have resulted in remarkable clinical benefits, including durable clinical responses and improved survival, in several tumor types. However, despite this important advancement, the benefit of immuno-oncology is limited to a minority of patients and only in a few indications. For example, following treatment with a programmed cell death-1 (PD-1) antibody, 31% to 34% of advanced melanoma patients (Weber et al, 2015; Robert et al, 2015), 19% to 20% of non-small cell lung cancer (NSCLC) patients (Borghaei et al, 2015; Brahmer et al, 2015; Herbst et al, 2016), and 25% of renal cell carcinoma (RCC) patients (Motzer et al, 2015) have durable objective (partial or complete) responses and improved overall survival (OS) compared with conventional therapies. Ipilimumab, a human monoclonal antibody (mAb) that blocks cytotoxic T-lymphocyte-associated antigen-4 (CTLA-4) on T cells (approved in 2011), achieves durable clinical responses in ~10% of patients with advanced melanoma and 5-year OS rates of ~18% (Hodi et al, 2010; Schadendorf et al, 2015; Maio et al, 2015). Both nivolumab and pembrolizumab, which are anti-PD-1 mAbs (approved in 2014), achieve clinical responses in 31% to 34% of advanced melanoma patients, and most responses are durable (Weber et al, 2015; Robert et al, 2015). While the activity observed with single-agent anti-PD-1 mAbs is significant, combined treatment with ipilimumab and nivolumab (approved in 2015) results in clinical

[figure not shown]
responses of 55% to 60% in metastatic melanoma patients (Ribas et al, 2017; Larkin et al, 2015). Similarly, nivolumab plus ipilimumab also showed significantly higher ORR compared with sunitinib (42% vs 27%) in previously untreated advanced RCC patients (Motzer et al, 2018). However, the improvement in clinical activity achieved with nivolumab in combination with ipilimumab is accompanied by increased side effects; Grade 3 or 4 events occurred in 59% of patients in the nivolumab plus ipilimumab group, in 21% of those in the nivolumab group, and in 28% in the ipilimumab group (Wolchok et al, 2017). Thus, there is a critical need for biomarkers that can predict which cancer patients will benefit from ipilimumab and nivolumab combination therapy.

2.2.2 Biomarkers to Predict Benefit from Treatment with Immune Checkpoint Inhibitors

Certain tumors are primed and ready to respond to treatment with an anti-PD-1 antibody, and others are not. Cancer patients who benefit from anti-PD-1 treatment are characterized as having “hot” tumors, whereas those who do not respond to anti-PD-1 treatment are characterized as having “cold” tumors. Several biomarkers have been proposed to classify a tumor as “hot” versus “cold,” including programmed cell death ligand-1 (PD-L1) expression, tumor mutation burden (Rizvi et al, 2015), interferon-gamma expression (Ayers et al, 2017), tumor immune signature (Chen et al, 2016), fecal microbiome profile (Gopalakrishnan et al, 2018), and the extent of the CD8 T-cell infiltrate (Hegde et al, 2016). These biomarkers have an association with the CD8 T-cell infiltrate (Maby et al, 2015; Thompson et al, 2017; Roy and Trinchieri, 2017). Several clinical studies have shown that clinical response to anti-PD-1 treatment is correlated with the pre-treatment number or the percentage of tumoral CD8 cells (Tumeh et al, 2014; Chen et al, 2016; Johnson et al, 2016). Therefore, larger numbers of tumoral CD8 cells may be a useful biomarker to identify “hot” (CD8 high) tumors.

Furthermore, an increase in tumoral CD8 cells has been observed after anti-PD-1 treatment, and this increase is associated with improved clinical outcomes in melanoma and squamous cell carcinoma of the head and neck (SCCHN; Chen et al, 2016; Concha-Benavente et al, 2017). Following anti-PD-1 treatment, a significant increase in intratumoral CD8 cells was seen in responders but not in non-responders (Figure 5).

[figure not shown]
Figure 5: Tumor-infiltrating CD8 T-cell Expression in Responders and Non-responders to PD-1 Blockade

Tumor samples were stained by immunohistochemistry with pooled data in panel A and representative images in panel B. Adapted from [Chen et al. 2016](#).

Treatment with ipilimumab monotherapy also results in an increase in CD4 and CD8 T cells in the tumor ([Gao et al, 2017](#); [Kvistborg et al, 2014](#)). In a preclinical tumor model, anti-CTLA-4 treatment of tumor-bearing animals resulted in a significant increase in intravascular CXCL9 and E-selectin expression, which are involved in mediating CD8 T-cell extravasation and entry into the tumor ([Wilson et al, 2016](#)). Therefore, adding ipilimumab to anti-PD-1 treatment could further promote the trafficking of CD8 T cells into the tumor microenvironment. This hypothesis is supported by recent finding in a small subset of participants from the CheckMate 038 study in which the combination of ipilimumab and nivolumab significantly induced higher percentage of tumoral CD8 cells compared with nivolumab alone ([Figure 6](#); [Ribas et al, 2017](#)). In addition, the combination of ipilimumab and nivolumab yielded a higher response rate compared with nivolumab alone ([Larkin et al, 2015](#)).

Figure 6: Tumor-infiltrating CD8 T-cell Expression by Best Overall Response

CR = clinical response; Ipi = ipilimumab; NE = not evaluable; Nivo = nivolumab; PD = progressive disease; PR = partial response; SD = stable disease.
Biomarker study on Phase 1b CheckMate 038 study and tumor biopsies were assessed by immunohistochemistry. Adapted from Ribas oral presentation at 2017 AACR.

[figure not shown]
In summary, both pre-treatment tumoral CD8 cells and recruitment of CD8 T cells in response to immune checkpoint inhibitors are associated with improved clinical outcomes in patients treated with anti-PD-1 therapy. These data suggest that a rational approach to convert “CD8 low tumors into “CD8 high tumors is through combination treatment approaches with anti-PD-1 and anti-CTLA-4 mAbs that can recruit more CD8 T cells to the tumor (Haanen, 2017).

A prospective study with larger sample size is warranted to confirm that the percentage of tumoral CD8 cells at the time of treatment can determine responsiveness to anti-PD-1 therapy and whether combination therapy can convert tumors from CD8 low to CD8 high. We propose a prospective clinical study in which patients with varying advanced solid tumors will be assigned to 1 of 2 treatment arms based on the percentage of tumoral CD8 cells at the time of treatment. Participants who have a tumor with $\geq 15\%$ CD8 cells (classified as CD8 high) will receive nivolumab monotherapy, and participants who have a tumor with $< 15\%$ CD8 cells (classified as CD8 low) will receive ipilimumab in combination with nivolumab.

It is well recognized that immune infiltration varies across tumor types, and different tumor types may display a range of therapeutic sensitivities. Several ongoing studies are evaluating nivolumab treatment in various tumor types (BMS Nivolumab Studies). To better assess the feasibility of using percent of tumoral CD8 cells as a biomarker for selecting checkpoint inhibitor therapy and to gain more insight regarding the design of the trial, we examined CD8 cells in a set of 195 tumor samples from 10 different tumor types (Figure 7). For tumor types in which anti-PD-1 treatment has been approved, the classification of CD8 high tumor is consistent with the clinical benefit reported. The 15% cutoff was selected based on data from retrospective

studies and evaluation of responses to checkpoint inhibitors. This study will advance the field by providing a prospective classification of CD8 high versus CD8 low tumors at the time of treatment, based on response to nivolumab, and address the predictive value of the CD8 biomarker for selecting patients who can benefit from nivolumab with or without ipilimumab.

Figure 7: Percentage of Tumoral CD8 T Cells by Immunohistochemistry in Different Tumor Types

ADC = adenocarcinoma; CRC = colorectal cancer; GBM = glioblastoma multiforme; HCC = hepatocellular carcinoma; IHC = immunohistochemistry; MSI = microsatellite instable; MSS = microsatellite stable; RCC = renal cell carcinoma; SCC = squamous cell carcinoma.

IHC is performed on formalin-fixed paraffin-embedded (FFPE) tumor samples obtained from a cohort of untreated cancer patients. Tumor tissues were fixed in 10% formalin, embedded in paraffin, and transversely sectioned; 4- μ m sections were used for the IHC study. Sections were stained with mouse anti-human monoclonal antibodies against CD8 (Thermo Scientific, MS-457-S). Quantitative analysis of IHC staining was conducted using the image analysis software ImageScope-Aperio/Leica. Five random areas (1 mm² each) were selected, and a customized software algorithm for each immunologic marker was used to determine the percentage of positive cells per high-power field. The data are expressed as a percentage score (total number of positive cells divided by the total number of cells and multiplied by 100). IHC staining was interpreted in conjunction with hematoxylin and eosin stained sections, which facilitated the identification of malignant cells and thus directed IHC quantification.

